24.0 Blood Draw
24.1 *Will blood be collected specifically for this research?
25.0 Blood Draw Details
25.1 *Source of Blood Samples (Check all that apply.)
☑ Subjects as part of a clinical trial
Blood Donors with a condition or a disease that are NOT part of a clinical trial
The Scripps Research Institute (TSRI) Normal Blood Donor Service (NBDS)
OTHER normal blood donors NOT part of the Normal Blood Donor Service (NBDS)
If Other, please explain where the samples are coming from:
(If you are using TSRI NBDS, be sure to include an NBDS Donor Information Form with your submission.)
25.2 *Describe in simple language how this blood will be used.
Blood samples will be used for serum pregnancy test (if female), complete metabolic panel (CMP), that includes gamma glutamyl transferase (GGT), and complete blood count with differential (CBC w/diff) for general bodily functioning. In addition, blood will be drawn for drug concentration and to assess the HPA-axis function (plasma cortisol and ACTH).
25.3 *How frequently will the blood samples be collected?
Less Than 2 Times per Week
O More Than 2 Times per Week
O N/A Outside Scripps
25.4 *How much blood (ml) will be collected each draw?
© Less Than 50 Mls (10 teaspoons)
C More Than 50 MIs (10 teaspoons)
O N/A Outside Scripps
25.5 *Who will draw the blood?
[name], our Research Medical Assistant who is a certified phlebotomist, will draw the blood samples.
25.6 If blood will be obtained outside of Scripps, will the samples be obtained with Informed Consent? (Note: If Yes, attach a copy of the IRB approval and/or approved Informed Consent from the other site to the Inital Review Submission Form.)
Yes
○ No
YE No. or leave a complete contents
If No, please explain why:

25.7 *Will the blood be used for genetic analysis?
∩ Yes No
25.8 If Yes, will the results of the genetic analysis be shared with subjects? (REMINDER: If you plan to share the results, consider adding the Genetic Information Nondiscrimination Act language to the consent. Please click on the grey 'Help' button in the upper right to view the genetic language template.)
O Yes O No
If Yes, explain how the results will be used:
25.9 *Will ALL blood samples used in the study be unidentified?
^{25.10} *Will leftover unidentified blood be used for other studies? (Future plans must first be reviewed by a Scripps IRB.)
C Yes O No
26.0 Subject Compensation
*Will subjects receive any payment or compensation for participation in this study?
26.1 *Will subjects receive any payment or compensation for participation in this study? © Yes © No
€ Yes ♥ No
© Yes © No 27.0 Subject Compensation Detail 27.1 *Describe all payments/reimbursement being offered to subjects, such as transportation expenses,
27.0 Subject Compensation Detail 27.1 *Describe all payments/reimbursement being offered to subjects, such as transportation expenses, meals, gifts, and other out-of-pocket expenses. Subjects will be reimbursed at the following rates: \$50 for the screening visit (Visit 1), \$75 for the randomization visit (Visit 2), \$150 for cue reactivity procedures (Visit 3), \$50 for the 1-week follow-up visit (Visit 4), and \$50 for the 1-month follow-up visit (Visit 5). Total compensation for
27.0 Subject Compensation Detail 27.1 *Describe all payments/reimbursement being offered to subjects, such as transportation expenses, meals, gifts, and other out-of-pocket expenses. Subjects will be reimbursed at the following rates: \$50 for the screening visit (Visit 1), \$75 for the randomization visit (Visit 2), \$150 for cue reactivity procedures (Visit 3), \$50 for the 1-week follow-up visit (Visit 4), and \$50 for the 1-month follow-up visit (Visit 5). Total compensation for completion of all 5 study visits is \$375.00. We provide taxi transportation for subjects who would otherwise be unable to participate in the study, to and from our laboratory at TSRI. We have a voucher system arranged with Yellow Cab specifically for this purpose. Estimates from our current human laboratory study indicate this will
27.0 Subject Compensation Detail 27.1 *Describe all payments/reimbursement being offered to subjects, such as transportation expenses, meals, gifts, and other out-of-pocket expenses. Subjects will be reimbursed at the following rates: \$50 for the screening visit (Visit 1), \$75 for the randomization visit (Visit 2), \$150 for cue reactivity procedures (Visit 3), \$50 for the 1-week follow-up visit (Visit 4), and \$50 for the 1-month follow-up visit (Visit 5). Total compensation for completion of all 5 study visits is \$375.00. We provide taxi transportation for subjects who would otherwise be unable to participate in the study, to and from our laboratory at TSRI. We have a voucher system arranged with Yellow Cab specifically for this purpose. Estimates from our current human laboratory study indicate this will apply to 20% of the 50 randomized subjects. How will subjects be paid? (Check all that apply.)
27.0 Subject Compensation Detail 27.1 *Describe all payments/reimbursement being offered to subjects, such as transportation expenses, meals, gifts, and other out-of-pocket expenses. Subjects will be reimbursed at the following rates: \$50 for the screening visit (Visit 1), \$75 for the randomization visit (Visit 2), \$150 for cue reactivity procedures (Visit 3), \$50 for the 1-week follow-up visit (Visit 4), and \$50 for the 1-month follow-up visit (Visit 5). Total compensation for completion of all 5 study visits is \$375.00. We provide taxi transportation for subjects who would otherwise be unable to participate in the study, to and from our laboratory at TSRI. We have a voucher system arranged with Yellow Cab specifically for this purpose. Estimates from our current human laboratory study indicate this will apply to 20% of the 50 randomized subjects. How will subjects be paid? (Check all that apply.) □ Cash □ Check from investigator, sponsor, CRO, or other outside entity □ Check request or payroll payment through Scripps (requires W-9 tax form)
27.0 Subject Compensation Detail 27.1 *Describe all payments/reimbursement being offered to subjects, such as transportation expenses, meals, gifts, and other out-of-pocket expenses. Subjects will be reimbursed at the following rates: \$50 for the screening visit (Visit 1), \$75 for the randomization visit (Visit 2), \$150 for cue reactivity procedures (Visit 3), \$50 for the 1-week follow-up visit (Visit 4), and \$50 for the 1-month follow-up visit (Visit 5). Total compensation for completion of all 5 study visits is \$375.00. We provide taxi transportation for subjects who would otherwise be unable to participate in the study, to and from our laboratory at TSRI. We have a voucher system arranged with Yellow Cab specifically for this purpose. Estimates from our current human laboratory study indicate this will apply to 20% of the 50 randomized subjects. How will subjects be paid? (Check all that apply.) □ Cash □ Check from investigator, sponsor, CRO, or other outside entity
27.0 Subject Compensation Detail 27.1 *Describe all payments/reimbursement being offered to subjects, such as transportation expenses, meals, gifts, and other out-of-pocket expenses. Subjects will be reimbursed at the following rates: \$50 for the screening visit (Visit 1), \$75 for the randomization visit (Visit 2), \$150 for cue reactivity procedures (Visit 3), \$50 for the 1-week follow-up visit (Visit 4), and \$50 for the 1-month follow-up visit (Visit 5). Total compensation for completion of all 5 study visits is \$375.00. We provide taxi transportation for subjects who would otherwise be unable to participate in the study, to and from our laboratory at TSRI. We have a voucher system arranged with Yellow Cab specifically for this purpose. Estimates from our current human laboratory study indicate this will apply to 20% of the 50 randomized subjects. How will subjects be paid? (Check all that apply.) Cash Check from investigator, sponsor, CRO, or other outside entity Check request or payroll payment through Scripps (requires W-9 tax form) Gift certificate

27.2	*How much will each subject be paid per visit? And in total?
See	e above
27.3	*Describe your plan for issuing subject payments: (For example: per visit, end of study, etc.)
Sub	ojects will be paid with a check at the end of each visit that they complete.
27.4	*Will there be any costs (such as prolonged hospitalization, extra tests, co-payments) to subjects associated with their participation in research?
0	Yes 🕙 No
If y	es, please explain.
27.5	Who will pay for the treatment of a research related injury?
	Sponsor
	Subject or his or her medical insurance
V	Other
	Not Applicable
If o	ther, describe.
	subject needs either medical care or urgent medical treatment as a result of their icipation in the study, TSRI general liability insurance will cover the costs.

28.0 Study Plan - Details

28.1 Research Methods - Include the Schedule of Events or provide a precise description of the data collection methods. (Attach the Schedule of Events to the Initial Review Submission Form, if applicable)

Overview of Study Design.

A total of 50 subjects per study will be randomly assigned to double-blind, subchronic dosing with active drug (n = 25) or matched placebo (n = 25). Subjects will meet the Diagnostic and Statistical Manual – 5th Edition (DSM V) criteria for alcohol use disorder of at least moderate severity (AUD-MS) and be non-treatment-seeking, to avoid exposing treatment-seeking individuals with AUD-MS to alcohol cues. Alcohol abstinence is required during the last 3 days of the dosing period in order to test the effect of study drug when motivational symptoms of early abstinence are manifest. Human lab testing occurs on the last day of dosing/third day of abstinence.

Subjects are presented with 12 positive, negative or neutral affective images selected from the International Affective Picture System on a flatscreen monitor (IAPS). Each affective condition is followed by in vivo exposure to the subject's preferred alcoholic beverage or bottled water, which the subject is told to view and smell for 90 seconds and to not drink it. Endpoints selected assess the effects of drug relative to placebo on responsivity to in vivo alcohol cue exposure in the lab, as well as on naturalistic measures of drinking, affect, and craving through 1-month posttreatment.

These methods inform the 3 stages of the addiction cycle: preoccupation/anticipation (craving), binge/intoxication (drinking quantity and frequency, binge drinking) and negative affect (mood, anxiety). Craving in response to alcohol cue exposure in the lab has been reliably predictive of subsequent drinking in alcoholics, and thus craving in response to in vivo alcohol cue exposure in the laboratory comprises the primary outcome for this proof-of-concept study. Self-reported drinking data are collected as a secondary outcome variable, as the 3-day abstinent interval constrains complete evaluation of this variable, and drinking data are collected under less

controlled conditions than craving in response to in vivo alcohol cue exposure in the lab.

Subjects return 1 week and 1-month after drug discontinuation to assess any persisting effects on naturalistic measures of drinking, craving and affect. A positive signal on such indices would lend support to the potential utility of the drug in the treatment of AUD-MS and identify endpoints likely to show a positive drug effect in clinical trials.

Study Procedures:

Visit 1-Screening: After providing written informed consent, subjects complete the Screening Visit for initial evaluation of eligibility. A mini-cue session familiarizes subjects with the human lab setting and identifies non- cue-reactive subjects for study exclusion (Visual Analogue Scale [VAS] craving rating of alcohol cue < 3 points higher than water cue).

Visit 2-Randomization: Subjects complete the evaluation for eligibility. Medically cleared subjects complete baseline assessments and are randomized to receive a blistercard containing the double-blind study drug. A phone call is scheduled for Day 3 (and Day 7 in studies having 8-10 days of drug exposure) to address any questions or concerns and assess compliance.

Visit 3-Human Lab Testing: The human lab session is conducted in the afternoon on the last day of dosing and will last for approximately 2 hours. Subjects are instructed to take their last dose of drug at 8 AM. Medication compliance will be assessed on the day of testing using returned pill count and confirmed retrospectively with drug plasma determinations. Abstinence from alcohol will be assessed with breath alcohol concentration (BAC) and Timeline Followback Interview (TLFB) and confirmed retrospectively via urinary ethyl glucuronide and ethyl sulfate (EtG/EtS) testing, which can reliably detect alcohol metabolites in urine 80 hours after alcohol consumption. Upon confirmation of eligibility and completion of clinical assessments, subjects will be escorted to a lighting-controlled, sound-attenuated room for mood induction and alcohol exposure. Our alcohol cue reactivity methods have been described above. A 3 (positive, neutral, negative affect) × 2 (alcohol, water) within-subjects, block-factorial design (6 repeated measures) will be employed for the cue reactivity manipulation. All six mood-beverage combinations will be presented to each subject. Order of affect-beverage combinations will be determined by computer-generated randomization code to control for potential order effects. Time-locked subjective and physiological data will be collected by computer in response to each affect-beverage pair. Upon completion of the study, subjects relax, are debriefed, and complete measures of craving and mood to verify a return to baseline.

Visits 4 and 5 – Follow-Up: Subjects return 1 week and 1 month after the lab session and discontinuation of study drug to assess persistence of any treatment effects and resolution of any adverse reactions. Motivational interviewing and potential treatment options are provided by a study clinician at Visit 5.

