Administration Instructions:	Administration and dosing instructions will be provided by the Study Coordinator to the subject. Subjects will be instructed to take 2 tablets (1 in the AM, 1 in the PM) a day, for every day leading up to their Cue reactivity session. They will be instructed to return any unused study medication upon their return to the laboratory.
	Safety information (such as not taking any supplemental or over-the-counter medications, not sharing the study medication with others, etc.) will also be provided, along with the study physician's emergency contact information in case of adverse events or side effects.
	Common adverse reactions (5% or greater) are diarrhea, nausea, headache and upper respiratory tract infections, which will be managed, if necessary, by interventions recommended by study physicians.
Possible Untoward Effects, Their Symptoms & Treatment:	Less commonly, depression and suicidal thoughts may occur. Subjects will be screened with the MINI diagnostic interview, Columbia Suicide Scale and Beck Depression Inventory-II to exclude at risk subjects from study participation, and mood will be systematically monitored through study completion.

Contraindications and Interactions, If Known: Contraindications are known hypersensitivity to apremilast or any excipients in formulation. Use with strong cytochrome P450 enzyme inducers may result in loss of efficacy and are disallowed by the study protocol.

$^{20.3}$ *Describe your plan for storing, dispensing and accounting for the study drug(s).

The medication is stored in a locked cabinet in the medication room that is kept locked at the Laboratory of Clinical Psychopharmacology. Our pharmacy technician will prepare and label blistercard packages of medication (apremilast and placebo) for the study. They will also keeps the randomization code and maintains record of study medications dispensed and returned throughout the study. The Study Coordinator will monitor medication compliance by recording the number of pills dispensed at randomization Visit 2 and returned at lab sessions Visit 3 (using returned blistercards) on a drug dispensation case report form.	
$^{20.4}$ *Name all persons who will dispense the study drug(s) and sign drug accountability record	ls.
[name] Study Coordinator	
20.5 *Has the investigational pharmacy been notified?	
O Yes	
If Not, please explain:	
20.6 Check all drugs that will be paid for by the sponsor or study budget.	

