37.0 Study Population	
*Briefly describe your targeted population. (Patients with a condition or disease, healthy control subjects, etc.)	
We are looking to recruit 50 paid, non-treatment-seeking, alcohol-dependent but otherwise healthy male and female volunteers between the ages of 18 and 65.	
37.2 *Explain rationale for using human subjects.	
The purpose of this study is to evaluate the efficacy of apremilast as a potential treatment for alcohol use disorder of moderate or greater severity; therefore, use of humans is essential to determining the efficacy of apremilast as a potential treatment in this disorder.	
37.3 *Age	
Age Range Not Applicable	
Enter the specific age range for study population.	
From:	
18	
To:	
65	
37.4 *Gender	

decreased craving for alcohol following alcohol cue exposure in the laboratory and report fewer symptoms of protracted abstinence (e.g., craving, relapse to drinking, mood and sleep

disturbances) under naturalistic conditions, relative to those treated with placebo. This will allow

O Male
⊕ Both male and female
37.5 *How many subjects are you planning to enroll at this institution/site?
50
If this is a chart review, indicate the number of charts: (If this is not a chart review, enter θ .)
0
If necessary, provide explanation below.
37.6 *How many subjects will be enrolled at ALL sites? (Include Scripps and NON-Scripps)
50
If necessary, provide explanation below.
37.7 To achieve your needed number of subjects, how many subjects do you estimate will need to give informed consent? (Allowing for screen failures)
100
37.8 *Justification for the number of subjects required:
Previous studies in our lab have shown that we need to give informed consent to 100 subjects in order to enroll the 50 subjects required for the study.
37.9 Please check all potentially vulnerable populations that are included:
* Regulated
Children / Minors (subjects less than 18 years) *
Pregnant Women *
Prisoners *
☐ Economically or educationally disadvantaged persons
Non-ENGLISH speaking
Diminished mental capacity
Physically disabled
☐ Students
Scripps Health Employees
Scripps Research Institute Employees
Other
If other, describe.

If including vulnerable subjects, explain why. Explain what safeguards are included to protect against coercion or undue influence.

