- Sexually active female subjects with childbearing potential who are pregnant, nursing, or refuse to use effective methods of birth control for the duration required by a specific protocol.
- No fixed domicile and/or no availability by home or mobile telephone.
- History of hypersensitivity to the study drug or the ingredients.
- · Failure to take double-blind medication as prescribed.

Exclusion Criteria:

- Active suicidal ideation, as systematically assessed with the Columbia Suicide Severity Rating Scale.
- Meets DSM-5 criteria for a major psychiatric disorder, including mood or anxiety disorders or substance use disorders other than alcohol or nicotine.
- Has a urine drug screen (UDS) positive for substances of abuse other than alcohol.
- Significant medical disorders that will increase potential risk or interfere with study participation as determined by the study physician.
- · History of seizure disorders.
- Liver function tests more than 3 times the upper limit of normal or elevated bilirubin.
- Treatment within the month prior to screening with (1) an investigational drug, (2) medications which may negatively interact with study medications, or (3) drugs that may influence study outcomes (e.g., disulfiram [Antabuse], naltrexone [ReVia], acamprosate [Campral], anticonvulsants, or antidepressants).
- Ongoing treatment with medications that may increase risk, including prescribed, over-the-counter, and herbal preparations, as determined by the study physician.
- Sexually active female subjects with childbearing potential who are pregnant, nursing, or refuse to use effective methods of birth control for the duration required by a specific protocol.
- No fixed domicile and/or no availability by home or mobile telephone.
- History of hypersensitivity to the study drug or the ingredients.
- Failure to take double-blind medication as prescribed.

9.1 *Will ANY specimens, other than blood, be obtained for this study? © Yes © No	Ographic.		

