NCT03175549

Medication Development in Alcoholism: Apremilast versus Placebo

Statistical Analysis Plan Date: 01/20/2017

Statistical Analysis Plan, Demographic and baseline clinical characteristics will be examined for group differences by Fisher's Exact test for categorical/dichotomous variables and ANOVA for continuous variables. Variables will be tested individually for correlation to each outcome variable by Pearson's product-moment correlation or χ^2 , as appropriate. Any variable significantly associated with outcome or differing between treatment groups will be evaluated in all subsequent analyses as a covariate and will be retained if it reduces the residual variance, or otherwise will be left out of the model. Potential covariates of interest include baseline value of a measure, baseline values of peripheral markers of inflammation and stress response, sex. family history of alcoholism, smoking, and age of onset of heavy drinking. 98,99,100 Hypothesis: Subjects treated with active drug (apremilast) will report significantly lower VAS craving ratings in response to in vivo alcohol cues during human lab testing than placebo treated subjects. Repeated measures mixed effects models (MEM)¹⁰¹ will be used to examine drugplacebo differences in VAS craving ratings in response to beverage exposure (alcohol vs. water), where drug is treated as a fixed, between-subjects variable and beverage presentation is the repeat measure. Beverage will be considered a fixed, within-subjects variable and subject as a random effect. Drug effects on naturalistic secondary outcomes, i.e., drinking, will be examined using repeat MEM, as above Safety evaluations: Rates of treatment-emergent signs and symptoms will be computed for each treatment group by body system (e.g., liver, hematologic). Changes and trends in laboratory results will be examined based on shift tables and scatter plots. Relationship to exposure (dose and time) to study drug will be examined. χ^2 analyses will be used to compare the drug groups on rate of study discontinuation due to adverse reactions and overall.

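### Plasma confirmation of compliance can expose a missed non-taker only on apremilast, and nothing in the plan stops the non-compliance exclusion from acting on it

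*Protocol*

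**What the plan says.** Protocol 28.1, under the Visit 3 lab session, sets two compliance checks: "Medication compliance will be assessed on the day of testing using returned pill count and confirmed retrospectively with drug plasma determinations". Protocol 20.3 describes the pill count as "recording the number of pills dispensed at randomization Visit 2 and returned at lab sessions Visit 3", using blister cards prepared for apremilast and placebo alike. Protocol 28.1 (Visit 2) adds a phone call "to address any questions or concerns and assess compliance", again in both arms. On the assay, Protocol 25.2 says only that "blood will be drawn for drug concentration"; no tracer or marker in the placebo capsules is mentioned.

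The exclusion criteria in Protocol section 37 include "Failure to take double-blind medication as prescribed". They give no threshold, no timing and no statement of which evidence counts.

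The SAP states the primary hypothesis ("Subjects treated with active drug (apremilast) will report significantly lower VAS craving ratings in response to in vivo alcohol cues") and a mixed effects model for it. It defines no analysis set, gives no handling of non-compliers, and has no rule for a plasma result that contradicts the pill count.

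**The concern.** The non-compliance exclusion can act only after randomisation, because double-blind medication is first issued at Visit 2. The protocol names plasma level as the confirming evidence of compliance and non-compliance as a ground for exclusion, and nothing keeps the two apart.

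Take a subject whose returned card looks complete but who did not take the capsules. On apremilast, the assay shows this. On placebo, it cannot. A set filtered on plasma therefore compares an apremilast arm cleared of such subjects with a placebo arm that still holds them. The arms then differ in adherence and in whatever goes with it, such as motivation or drinking severity. What is at stake is the primary craving contrast in a proof-of-concept study with 25 subjects per arm.

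Simply adding a per-protocol set would not settle the matter if that set used the protocol's own two-step definition of compliance, because the asymmetry would carry over into it.

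**Working it through.** **The plan's figures.** The documents give no compliance rate and no figure for this point. The only size stated is 25 per arm (Protocol 28.1). Its justification in Protocol 37.8 is screening yield ("we need to give informed consent to 100 subjects in order to enroll the 50 subjects required for the study"), so there is no effect size, SD, alpha or power to reproduce. The attachment list names correspondence on power whose content is not in the documents, and I do not count that against the plan.

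**Assumptions (none is in the documents).** Two-sided test at 5%; craving in SD units; a two-sample t comparison in place of the mixed model; no drug effect. Let q be the share of subjects who pass the pill count but did not take the capsules, the same in both arms. Let d be how much more they crave than takers.

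**Bias.** With takers' mean m, plasma filtering leaves an apremilast mean of m. The placebo mean stays at m + q·d. So

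bias (apremilast minus placebo) = m − (m + q·d) = −q·d.

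- Smallest corner: 0.10 × 0.3 = 0.03 SD.
- Largest corner: 0.20 × 0.8 = 0.16 SD.
- d = 0: no bias. d < 0: the sign reverses.

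**Error rate.** With n₁ = 25(1 − q) and n₀ = 25, SE = √(1/n₁ + 1/n₀), and the rejection rate comes from the non-central t with non-centrality q·d/SE. For q = 0.20, SE = √(1/20 + 1/25) = 0.300. For q = 0.10, SE = √(1/22.5 + 1/25) = 0.291.

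| q | d | bias (SD) | non-centrality | two-sided error | error in the drug's favour |
|---|---|---|---|---|---|
| 10% | 0.3 | 0.03 | 0.10 | 5.1% | 3.2% |
| 10% | 0.5 | 0.05 | 0.17 | 5.3% | 3.7% |
| 20% | 0.5 | 0.10 | 0.33 | 6.2% | 5.1% |
| 20% | 0.8 | 0.16 | 0.53 | 8.2% | 7.5% |
| 20% | −0.5 | −0.10 (against the drug) | −0.33 | 6.2% | 1.1% |

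The nominal values are 5.0% and 2.5%.

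**What the pill count does.** Let r be all non-takers and s the share of them that the pill count catches in both arms. The hidden share left on placebo is h = r(1 − s)/(1 − r·s), and the bias is −h·d. Take r = 20% and d = 0.5, using a normal approximation that also allows for the extra spread on placebo:

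- s = 0: h = 0.20, bias −0.10 SD, two-sided error 6.3%.
- s = 0.5: h = 0.10/0.90 = 0.111, bias −0.056 SD. Expected losses are 5.0 of 25 on apremilast and 2.5 of 25 on placebo. SE = 0.309, two-sided error 5.4%.
- s = 1: 5 and 5 removed, bias 0, error 5.0%.

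**After the fix.** If all randomised subjects with lab data are analysed whatever the plasma result, plasma causes no differential removal. This source of bias is then zero at every q and d.

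**The case against.** The strongest reply is that the plan never says a plasma result excludes anyone. Protocol 28.1 puts the pill count on the day of testing and the plasma check afterwards. Subjects enter the cue room once eligibility is confirmed, when only the pill count is to hand. On that reading, the exclusion acts before the session on a measure common to both arms, and the SAP filters on nothing. This stands as far as it goes: a reader might infer that the protocol prescribes removal by plasma level, and the documents do not support that. They leave the consequence of a plasma result unstated. That leaves the route open, because exclusion is the only consequence they attach to non-compliance.

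A reader might also infer that subjects would be lost from one arm only. That is wrong: the pill count and the phone call apply to both arms, and only non-takers whom they miss are treated unequally.

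Nor can one infer that the bias favours apremilast. The documents say nothing about craving in non-takers.

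Finally, the size is modest. The bias of 0.03-0.16 SD compares with a standard error of about 0.29-0.30 SD, and the top of the range needs one subject in five to pass the pill count, fail the assay and crave 0.8 SD more. This also stands.

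**Conclusion.** The concern holds as a gap in the rules. Plasma confirmation is informative about non-taking only in the apremilast arm, a post-randomisation non-compliance exclusion exists, and neither document prevents the second from acting on the first. Whether bias would follow, and in which direction, cannot be known from the documents. Under the assumed 10-20% hidden non-takers and 0.3-0.8 SD higher craving, it would be 0.03-0.16 SD in the drug's favour with a two-sided error of 5.1-8.2%; with lower craving in non-takers, it would go against the drug. If the drug works, filtering the active arm would also change the question, from the effect in all randomised subjects to one in subjects with confirmed exposure on one side only. The likely size is small, but so is the cost of closing the gap, and the primary outcome is affected.

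**What to change.** In the SAP and in the Visit 3 text of Protocol 28.1:

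- State that the primary between-arm analysis includes all randomised subjects with lab-session data, whatever the plasma result, and that plasma levels do not trigger the non-compliance exclusion.
- Base any supportive compliance set on returned pill count, with the same cut-off in both arms, fixed before unblinding. Label it a non-randomised comparison: it is still selected after randomisation, and Protocol section 20 lists diarrhea and nausea as common reactions, so stopping capsules may itself differ by arm.
- Use plasma levels to describe exposure within the apremilast arm, for example the proportion with detectable drug and a plot of craving against concentration.
- Allow a plasma-restricted between-arm analysis only if it is labelled exploratory and asymmetric.

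The cost is wording; no new data are needed. The downside is that apremilast non-takers who are kept dilute the estimated drug effect. If they get no effect, and 10-20% of the arm are such subjects, the estimate is 90-80% of the effect in takers (1 − q). This dilution arises in the apremilast arm only, since placebo has no drug effect to dilute.
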